7.6. Special Situations Reports

7.6.1. Definitions of Special Situations

Special situation reports include all reports of medication error, abuse, misuse, overdose, reports of adverse events associated with product complaints, occupational exposure with an AE, and pregnancy reports regardless of an associated AE and AE in an infant following exposure from breastfeeding.

Medication error is any unintentional error in the prescribing, dispensing, or administration of a medicinal product while in the control of the health care provider, subject, or consumer.

Abuse is defined as persistent or sporadic intentional excessive use of a medicinal product by a subject.

Misuse is defined as any intentional and inappropriate use of a medicinal product that is not in accordance with the protocol instructions or the local prescribing information.

An overdose is defined as an accidental or intentional administration of a quantity of a medicinal product given per administration or cumulatively which is above the maximum recommended dose as per protocol or in the product labelling (as it applies to the daily dose of the subject in question). In cases of a discrepancy in drug accountability, overdose will be established only when it is clear that the subject has taken the excess dose(s). Overdose cannot be established when the subject cannot account for the discrepancy except in cases in which the investigator has reason to suspect that the subject has taken the additional dose(s).

Product complaint is defined as complaints arising from potential deviations in the manufacture, packaging, or distribution of the medicinal product.

Occupational exposure with an AE is defined as exposure to a medicinal product as a result of one's professional or non-professional occupation.

7.6.2. Instructions for Reporting Special Situations

7.6.2.1. Instructions for Reporting Pregnancies

The investigator should report pregnancies in female study subjects that are identified after initiation of study medication and throughout the study, including the post study drug follow-up period, to the Gilead DSPH using the pregnancy report form within 24 hours of becoming aware of the pregnancy.

Refer to Section [7.3](#) and the CRF/eCRF completion guidelines for full instructions on the mechanism of pregnancy reporting.

The pregnancy itself is not considered an AE nor is an induced elective abortion to terminate a pregnancy without medical reasons.

Any premature termination of pregnancy (eg, a spontaneous abortion, an induced therapeutic abortion due to complications or other medical reasons) must be reported within 24 hours as an SAE. The underlying medical reason for this procedure should be recorded as the AE term.

A spontaneous abortion is always considered to be an SAE and will be reported as described in Sections 7.1.1 and 7.1.2. Furthermore, any SAE occurring as an adverse pregnancy outcome post study must be reported to Gilead DSPH.

The subject should receive appropriate monitoring and care until the conclusion of the pregnancy. The outcome should be reported to Gilead DSPH using the pregnancy outcome report form. If the end of the pregnancy occurs after the study has been completed, the outcome should be reported directly to Gilead DSPH. Gilead DSPH contact information is as follows:

Email: PPD and Fax: PPD

Pregnancies of female partners of male study subjects exposed to Gilead or other study drugs must also be reported and relevant information should be submitted to Gilead DSPH using the pregnancy and pregnancy outcome forms within 24 hours. Monitoring of the subject should continue until the conclusion of the pregnancy. If the end of the pregnancy occurs after the study has been completed, the outcome should be reported directly to Gilead DSPH, fax number PPD or email PPD

Refer to [Appendix 5](#) for Pregnancy Precautions, Definition for Female of Childbearing Potential, and Contraceptive Requirements.

7.6.2.2. Reporting Other Special Situations

All other special situation reports must be reported on the special situations report form and forwarded to Gilead DSPH within 24 hours of the investigator becoming aware of the situation. These reports must consist of situations that involve study IMP and/or Gilead concomitant medications, but do not apply to non-Gilead concomitant medications.

Special situations involving non-Gilead concomitant medications does not need to be reported on the special situations report form; however, for special situations that result in AEs due to a non-Gilead concomitant medication, the AE should be reported on the AE form.

Any inappropriate use of concomitant medications prohibited by this protocol should not be reported as “misuse,” but may be more appropriately documented as a protocol deviation.

Refer to Section 7.6.2 and the CRF/eCRF completion guidelines for full instructions on the mechanism of special situations reporting.

All clinical sequelae in relation to these special situation reports will be reported as AEs or SAEs at the same time using the AE CRF/eCRF and/or the SAE report form. Details of the symptoms and signs, clinical management, and outcome will be reported, when available.

8. STATISTICAL CONSIDERATIONS

8.1. Analysis Objectives and Endpoints

8.1.1. Analysis Objectives

[figure not shown]
The primary objectives of this switch study are as follows:

- To evaluate the safety and tolerability of TAF 25 mg QD at Week 24
- To measure the proportion of subjects achieving virologic response (HBV DNA < 20 IU/mL) at Week 24

The secondary objectives of this switch study are as follows:

- To evaluate the safety and tolerability of TAF 25 mg QD at Weeks 48 and 96
- To measure the proportion of subjects achieving virologic response (HBV DNA < 20 IU/mL) at Weeks 48 and 96
- To evaluate biochemical (ALT normal and ALT normalization) and serological (loss of HBeAg with seroconversion to anti-HBe in HBeAg-positive subjects and loss of HBsAg with seroconversion to anti-HBs) responses at Weeks 24, 48, and 96
- To evaluate the effect of TAF 25 mg QD on renal parameters at Weeks 24, 48, and 96 in subjects with moderate or severe renal impairment and hepatically impaired subjects
- To evaluate the safety of TAF 25 mg QD as determined by percentage change in hip and spine bone mineral density (BMD) at Weeks 24, 48, and 96
- To evaluate the effect of TAF 25 mg QD on fibrosis as assessed by Fibrotest[®] at Weeks 24, 48, and 96
- To evaluate the effect of TAF 25 mg QD on changes in Child-Pugh-Turcotte (CPT) and Model for End-stage Liver Disease (MELD) scores at Weeks 24, 48, and 96 in hepatically impaired subjects
- To evaluate the pharmacokinetics of TAF and TFV

The exploratory objectives of this switch study are as follows:

8.1.2. Primary Endpoint

- The primary safety endpoint is the incidence of graded adverse events and graded laboratory abnormalities at Week 24.
- The primary efficacy endpoint is the proportion of subjects achieving virologic response (plasma HBV DNA < 20 IU/mL) at Week 24.

8.1.3. Secondary Endpoint

[figure not shown]
The Secondary safety endpoints are:

[figure not shown]
- Incidence of graded adverse events and graded laboratory abnormalities at Week 48 and 96
- Change from baseline in eGFR_{CG} at Weeks 24, 48, and 96 in subjects with moderate or severe renal impairment and hepatically impaired subjects
- Percent change from baseline in hip and spine bone mineral density (BMD) at Weeks 24, 48, and 96

The Secondary efficacy endpoints are:

- Proportion of subjects achieving virologic response (plasma HBV DNA < 20 IU/mL) at Weeks 48 and 96
- Proportion of subjects with plasma HBV DNA < 20 IU/mL and target detected/not detected (i.e. < LLOD) at Weeks 24, 48, and 96
- Proportion of subjects with serological response (loss of HBsAg and seroconversion to anti-HBs, loss of HBeAg and seroconversion to anti-HBe in HBeAg-positive subjects) at Weeks 24, 48, and 96
- Proportion of subjects with biochemical response (normal ALT and normalized ALT) at Weeks 24, 48, and 96
- Change in fibrosis as assessed by FibroTest[®] at Weeks 24, 48, and 96
- Change from baseline in CPT score ([Appendix 7](#)) and MELD score at Weeks 24, 48, and 96 in hepatically impaired subjects

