- 13) Use of investigational agents within 3 months of Screening, unless allowed by the Sponsor
- 14) Use of any prohibited medication as described in Section 5.3.

Part A Only (renal impairment):

- 1) Current or historical evidence of clinical hepatic decompensation (e.g., ascites, encephalopathy or variceal hemorrhage)
- 2) Abnormal hematological and biochemical parameters, including:
 - Hemoglobin < 9 g/dL
 - Absolute neutrophil count < 750/mm³
 - Platelets ≤ 50,000/mm³
 - AST > 10 × ULN
 - Albumin < 3.0 g/dL
 - Total bilirubin > 2.5 × ULN
 - INR > 1.5 × ULN (unless stable on anticoagulant regimen)
- 3) Subjects with ESRD (i.e. eGFR_{CG} < 15 mL/min) not on HD, or those on other forms of renal replacement therapy (i.e. peritoneal dialysis)

Part B Only (hepatic impairment):

- 1) Active variceal bleeding within 6 months or prior placement of a portosystemic shunt (such as transjugular intrahepatic portosystemic shunt [TIPS])
- 2) History of hepatorenal syndrome, hepatopulmonary syndrome, Grade 3 or Grade 4 hepatic encephalopathy, or spontaneous bacterial peritonitis within 6 months of Screening

- 3) Grade 2 hepatic encephalopathy at Screening
- 4) MELD score ≥ 30
- 5) Abnormal hematological and biochemical parameters, including
 - Absolute neutrophil count $< 750/\text{mm}^3$
 - Platelets $< 30,000/\text{mm}^3$
 - Hemoglobin $< 8.0 \text{ g/dL}$

Study Procedures/
Frequency:

- Screening Visit
- Treatment Period Visits: Baseline/Day 1, Weeks 4, 8, 12, 24, 36, 48, 60, 72, and 96/Early Discontinuation (ED)
- Subjects in Part A (renally impaired) who permanently discontinue study drug (either prematurely or after completing 96 weeks of treatment) for reasons other than HBsAg loss with confirmed seroconversion to anti-HBs will be followed every 4 weeks for 24 weeks off treatment or until initiation of appropriate, alternative HBV therapy, whichever occurs first. Use of appropriate, alternative HBV therapy is strongly encouraged.
- For subjects in Part B (hepatic impairment) who permanently discontinue study drug, immediate initiation of appropriate, alternative HBV therapy is strongly recommended.
- Review of concomitant medications, assessment for adverse events, and vital signs and weight measurement will be conducted at all study visits.

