Change from baseline in serum creatinine was the third key alpha-controlled safety endpoint. Overall, increases from baseline in mean values for serum creatinine were smaller in the TAF group compared with the TDF group. Mean (SD) changes from baseline at Week 48 were 0.010 (0.1140) mg/dL for the TAF group and 0.024 (0.0974) mg/dL for the TDF group ($p = 0.012$). Graded serum creatinine abnormalities were reported for 6 subjects (0.7%) in the TAF group; all of which were Grade 1 or 2. Of the 6 subjects, 5 subjects had isolated serum creatinine elevations that were not associated with decreased eGFR. One subject, who had a relevant medical history of hypertension and diabetes, had multiple instances of graded creatinine elevations and $eGFR \leq 50$ mL/min. No subjects in the TDF group had graded serum creatinine elevations.

In the TAF group, decreases from baseline in median $eGFR_{CG}$ values were significantly smaller compared with the TDF group. Median (Q1, Q3) changes from baseline at Week 48 were -1.2 ($-8.4, 7.5$) mL/min in the TAF group and -5.4 ($-12.0, 3.0$) mL/min in the TDF group ($p < 0.001$). The overall number of subjects who had any confirmed renal laboratory abnormality (ie, confirmed increases from baseline in creatinine of at least 0.5 mg/dL, or $eGFR_{CG}$ below 50 mL/min, or confirmed phosphorus < 2 mg/dL, was small (TAF 0.6%, 5 subjects; TDF 1.6%, 7 subjects). Most instances were isolated, transient, and resolved without treatment.

Summary of Proteinuria by Urinalysis (Dipstick) and by Quantitative Assessment

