- CPT score ([Appendix 7](#)) of 7-12 (inclusive) OR a past history of CPT score ≥ 7 and any CPT score ≤ 12 at Screening
- eGFR_{CG} $\geq 30 \text{ mL/min}$ using the Cockcroft-Gault equation {[Cockcroft 1976](#)}:

- eGFR_{CG} is calculated by:

$$\frac{(140 - \text{age in years}) (\text{actual body weight [kg]})}{(72) (\text{serum creatinine [mg/dL]})}$$

(Note: multiply estimated rate by 0.85 for women)

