6.3.4. Week 24 (visit window is –7 days)

- Complete physical examination with vital signs (blood pressure, pulse, respiration rate and temperature) and body weight
- Review concomitant medications
- Review adverse events
- Blood sample for serum chemistry and liver function tests (including PT/INR), hematology, plasma HBV DNA level, serum HBsAg (quantitative), HBV serology (qualitative HBsAg and HBeAg), eGFR_{CG}, virology (resistance surveillance), vitamin D assessment, and serum and plasma for storage

- Blood samples for Sparse PK:
 - All subjects except Part A, Cohort 2 (ESRD subjects on HD)
 - Single plasma PK sample
 - Part A, Cohort 2 Subjects (ESRD subjects on HD at selected sites)
 - On the day of hemodialysis, 4 samples will be collected:
 - 1 sample collected within 10 minutes before a hemodialysis session begins
 - 1 sample each collected approximately 1 hour prior to conclusion of the hemodialysis session from both the arterial and venous sides of the dialyzer and
 - 1 sample collected within 10 minutes after a hemodialysis session concludes

On the day of hemodialysis, study drug should not be administered to subjects until after the completion of hemodialysis and collection of any required post-hemodialysis samples for Part A, Cohort 2.

- Blood sample for Fibrotest[®]
- CPT ([[Appendix 7](#)] Assessment requires: total bilirubin, albumin, PT/INR, Ascites assessment, and Hepatic encephalopathy assessment) for Part B subjects (hepatic impairment) only
- MELD Score (Assessment requires: total bilirubin, serum creatinine, serum sodium, and PT/INR) for Part B subjects (hepatic impairment) only
- Fasting blood sample for serum bone biomarkers and metabolic assessment (glucose and lipid panel [total cholesterol, HDL, direct LDL, and triglycerides]) – no food or drinks, except water, at least 8 hours prior to blood collection
- Fasting urine sample for renal biomarkers for all subjects except Part A Cohort 2 (ESRD subjects on HD) – no food or drinks, except water, at least 8 hours prior to blood collection
- DXA scan of hip and spine (within –14 days of the expected visit date)
- Health Related Quality of Life (HRQoL) Surveys (CLDQ, SF-36, WPAI, EQ-5D-3L)
- Site-administered questions for Health Utilization Assessment to be completed

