7.5.6. Management of Potential Nephrotoxicity

For subjects with moderate or severe renal impairment (Part A, Cohort 1), and subjects with hepatic impairment (Part B), eGFR_{CG} will be followed post-baseline during the study.

eGFR_{CG} is calculated by:

$$\frac{(140 - \text{age in years}) (\text{actual body weight [kg]})}{(72) (\text{serum creatinine [mg/dL]})}$$

(Note: multiply estimated rate by 0.85 for women)

Any subject with a post baseline eGFR_{CG} < 15 mL/min must have serum creatinine measured again within 3 calendar days of receipt of results. At the time of this repeat serum creatinine assessment, serum Cystatin C will also be measured and the eGFR by CKD-EPI (cystatin C) will be calculated and compared with the baseline measurement. Any subject who has an eGFR_{CG} < 15 mL/min who also experiences > 20% reduction in eGFR by CKD-EPI (cystatin C) from baseline or any subject who has other clinical and/or laboratory evidence of acute renal failure will be discussed with the Medical Monitor and may require discontinuation from study drugs.

CKD-EPI (cystatin C) formula adjusted for age and sex:

$$\text{eGFR (mL/min/1.73m}^2\text{)} = 133 \times \min(\text{Scys}/0.8, 1)^{-0.499} \times \max(\text{Scys}/0.8, 1)^{-1.328} \times 0.996^{\text{Age}}$$

[× 0.932 if female],

where Scys is serum cystatin C (mg/L), min (Scys/0.8,1) indicates the minimum of Scys/0.8 or 1, and max (Scys/0.8,1) indicates the maximum of Scys/0.8 or 1.

If the eGFR_{CG} is confirmed to be < 15 ml/min and hemodialysis is to be initiated, the subject can remain on study after discussion with the Medical Monitor. However, any subject with eGFR < 15 mL/min who does not initiate hemodialysis, or those who initiate other forms of renal support (e.g. peritoneal dialysis) will be required to permanently discontinue study drug.

All subjects with moderate or severe renal impairment with a change from baseline serum creatinine of ≥ 0.4 mg/dL must have serum creatinine repeated, with a concurrent urinalysis and urine chemistry, within 2 weeks of receipt of results. If a subject has a confirmed change from baseline serum creatinine of ≥ 0.4 mg/dL, the Medical Monitor should be notified and a consultation with a nephrologist should be obtained.

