Appendix 7. Child-Pugh-Turcotte Score {Pugh 1973}

Parameter	Points Assigned		
	1	2	3
Albumin	> 3.5 g/dL (35 g/liter)	2.8 - 3.5 g/dL (28 to 35 g/liter)	< 2.8 g/dL (< 28 g/liter)
Ascites	Absent	Slight	Moderate to Severe
Bilirubin	< 2 mg/dL (< 34.2 micromol/liter)	2 - 3 mg/dL (34.2 to 51.3 micromol/liter)	> 3 mg/dL (> 51.3 micromol/liter)
Encephalopathy	None	Grade 1 – 2	Grade 3 - 4
Prothrombin time			
Seconds over control	< 4	4 – 6	> 6
INR	< 1.7	1.7 – 2.3	> 2.3

Modified Child-Pugh-Turcotte classification of the Severity of Liver Disease

	Class A	Class B	Class C
Total Points	5-6	7-9	10-15
Severity of Hepatic Cirrhosis	Well-compensated	Significant Functional Compromise	Decompensated
1- and 2- year survival	100% and 85%	80% and 60%	45% and 35%

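### Part B's renal endpoint, change in eGFR_CG, uses actual body weight with no ascites exclusion, so fluid shifts move it the wrong way at constant creatinine; a fixed-weight sensitivity summary is missing

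*Protocol*

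**What the plan says.** Protocol Section 8.1.3 names as a secondary safety endpoint "Change from baseline in eGFR_{CG} at Weeks 24, 48, and 96 in subjects with moderate or severe renal impairment and hepatically impaired subjects". The matching secondary objective is in Section 2.

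The Cockcroft-Gault formula, printed in Sections 4.2 and 7.5.6, takes "actual body weight [kg"] as its weight term. Section 7.5.6 applies it to Part B after baseline: for "subjects with hepatic impairment (Part B), eGFR_{CG} will be followed post-baseline during the study". The synopsis states that "vital signs and weight measurement will be conducted at all study visits", and Appendix 2 schedules body weight at each visit.

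Part A excludes current or past ascites (Section 4.3). Part B has no such exclusion. It admits CPT scores of 7 to 12, or "a past history of CPT score ≥ 7 and any CPT score ≤ 12 at Screening" (Section 4.2). Appendix 7 scores ascites up to "Moderate to Severe". At Weeks 24, 48 and 96 the CPT score requires "total bilirubin, albumin, PT/INR, Ascites assessment, and Hepatic encephalopathy assessment", but nothing links the ascites finding to the eGFR_CG analysis. No dry weight, fixed weight or ascites adjustment appears in either document.

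The synopsis (Statistical Methods) also plans descriptive change summaries for eGFR_CKD-EPI and serum creatinine. Section 8.6.2, the secondary safety analysis, lists neither. It also restricts the eGFR_CG summary to moderate or severe renal impairment, leaving out the hepatically impaired subjects whom Section 8.1.3 includes.

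**The concern.** At a given age, sex and creatinine, Cockcroft-Gault is proportional to weight. In a population where ascites can form or resolve, weight can change for reasons unrelated to the kidney, and the sign is perverse. A subject whose liver disease improves and who sheds fluid is scored as losing renal function; one who decompensates and accumulates fluid is scored as gaining it. The error therefore tracks liver status, which is itself assessed by CPT and MELD at the same visits. The LOCF analysis planned for eGFR_CG in Section 8.3 could carry a fluid-inflated value forward for a subject who leaves while decompensating.

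The potential for better renal safety is part of the rationale for studying TAF in Part B (Sections 1.3 and 1.4). With about 30 subjects and no control arm, nothing in the design cancels such an artefact, and no rule says how to read the renal measures if they disagree.

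**Working it through.** **Inputs from the documents.** Formula: (140 − age) × weight / (72 × creatinine), times 0.85 for women. Part B eligibility: eGFR_CG of at least 30 mL/min, with no upper limit (Section 4.2). Part B size: about 30. Phase 3 yardstick (Section 1.2.3): "Median (Q1, Q3) changes from baseline at Week 48 were -1.2" mL/min on TAF, with quartiles −8.4 and 7.5, against −5.4 mL/min on TDF.

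**Assumptions, since the plan gives no figure.** Body weight 70 kg; weight changes of 5 and 10 kg; baseline eGFR_CG of 30 to 120 mL/min; each visit's weight used in the formula.

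No planned figure needs reproducing: there is no sample size, power or margin for this endpoint, and the Phase 3 medians cannot be rebuilt without subject data.

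**Step 1, yardstick.** −1.2 − (−5.4) = 4.2 mL/min.

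**Step 2, one subject at constant creatinine.** Change in eGFR_CG = baseline eGFR_CG × (weight change / baseline weight). For 5 kg, 5/70 = 7.1%; for 10 kg, 10/70 = 14.3%. The weight change that equals the yardstick is 4.2 / baseline eGFR_CG.

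| Baseline eGFR_CG (mL/min) | Shift for 5 kg | Shift for 10 kg | Weight change equal to 4.2 mL/min |
|---|---|---|---|
| 30 | 2.1 | 4.3 | 14.0% (9.8 kg) |
| 60 | 4.3 | 8.6 | 7.0% (4.9 kg) |
| 80 | 5.7 | 11.4 | 5.3% (3.7 kg) |
| 90 | 6.4 | 12.9 | 4.7% (3.3 kg) |
| 120 | 8.6 | 17.1 | 3.5% (2.5 kg) |

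A 5 kg change reaches 4.2 mL/min only when baseline eGFR_CG is at least 4.2 / (5/70) = 58.8 mL/min.

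**Step 3, masking.** At 70 kg and creatinine 1.0 mg/dL, a 5 kg gain exactly offsets a creatinine rise to 75/70 = 1.07 mg/dL. That rise of 0.07 is about three times the mean Phase 3 change on TDF, 0.024 mg/dL (Section 1.2.3).

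**Step 4, the group mean.** If a fraction f of subjects change by 5 kg in the same direction and the rest do not change, the mean moves by f × baseline × 5/70.

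- Baseline 60: 1.1 mL/min for f = 25%, 2.1 for 50%, 3.2 for 75%.
- Baseline 90: 1.6, 3.2 and 4.8 mL/min.

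**Step 5, changes in no common direction.** Assuming normality, the Phase 3 TAF quartiles imply an SD of (7.5 + 8.4)/1.349 = 11.8 mL/min. With n = 30 the 95% half-width of a mean is 1.96 × 11.8/√30 = 4.2 mL/min. A weight-change SD of 3 kg at baseline 90 contributes 90 × 3/70 = 3.9 mL/min, so the total SD becomes √(11.8² + 3.9²) = 12.4 mL/min.

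**Step 6, weight held at Baseline.** The weight ratio is 1, so the shift at constant creatinine is 0 apart from ageing.

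**The case against.** The strongest reply is that the plan already contains the answer. The synopsis plans change summaries for serum creatinine and eGFR_CKD-EPI. SAP Section 4 applies the creatinine correction to the CKD-EPI estimate, and routine cystatin C is scheduled only at Baseline (Appendix 2), so the planned CKD-EPI change is evidently creatinine-based and available by visit. The cystatin C version printed in Section 7.5.6 has no weight term; the creatinine version is not printed, and I take it to have none. Section 8.8 also plans urinary renal biomarkers for Part B. A careful reader of all these outputs could see whether eGFR_CG moved without creatinine. This stands as partial mitigation. It does not correct the named endpoint, and Section 8.6.2 lists neither creatinine nor eGFR_CKD-EPI.

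The second reply concerns size. A reader might infer that fluid shifts would swamp the TAF-TDF difference from Phase 3. The documents do not support that. The 4.2 mL/min is a gap between group medians in another population, this study has no TDF arm, and Phase 3 quartiles of −8.4 and 7.5 show that individual changes above 4.2 are ordinary. The synopsis specifies a summary that includes the median and quartiles, which a few fluid shifts would barely move. Near the eligibility floor of 30 mL/min, 5 kg gives only half the yardstick.

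Third, two premises are uncertain. Use of each visit's weight is an inference from the formula plus weighing at every visit. The SAP text available refers to a main SAP (its Section 3.8.1 and Tables 3-2 to 3-8) whose derivation rules are not in the documents, so a fixed-weight rule could exist there. The prevalence of ascites is also unknown: the past-history route admits subjects who are compensated at Screening, and the references to diuretics and paracentesis in Appendix 4 are generic grading text.

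Finally, a fixed-weight eGFR_CG is close to a rescaled reciprocal of creatinine. That is true, but it shows directly, in mL/min, how much of the endpoint's movement is due to weight.

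**Conclusion.** The point holds in a limited form. As apparently defined, the named Part B renal endpoint responds to body fluid in the wrong direction at constant creatinine. At an assumed 70 kg, 5 kg moves an individual value by 7.1%, or 2.1, 4.3 and 5.7 mL/min at baselines of 30, 60 and 80. A material shift in the Part B mean needs many subjects to change the same way; otherwise the effect is a modest loss of precision (SD about 11.8 to 12.4 mL/min under the stated assumptions).

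Two stronger conclusions are tempting and unsupported. One is that Part B cannot separate renal function from fluid shifts: eGFR_CG alone cannot, but the planned set of measures partly can. The other is that a fixed-weight version should become the sole basis for the Part B renal conclusion. That would trade one imperfect measure for another in a descriptive study.

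The mismatch between Sections 8.1.3 and 8.6.2 over hepatically impaired subjects rests on no assumption and should be corrected in any case.

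**What to change.** Keep change in eGFR_CG as the endpoint. For Part B:

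- Add a sensitivity summary of change from baseline in eGFR_CG at Weeks 24, 48 and 96 with weight held at its Baseline value.
- Present it beside the as-planned eGFR_CG, the creatinine-based eGFR_CKD-EPI and the serum creatinine changes.
- State in advance that an eGFR_CG change not seen in the weight-free measures will not be read as a change in renal function.
- Add hepatically impaired subjects to Section 8.6.2 so that it agrees with Section 8.1.3.
- State which weight enters the post-baseline calculation. If the main SAP already fixes weight at Baseline, saying so closes the weight question.

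The cost is one derived variable and one table from weights and creatinine already collected, with no extra sampling. There are two limits: true lean-mass change is also held constant, and Baseline weight may itself include ascites, so the mL/min scaling can be off for some subjects.
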